- p Samples for future analysis will be collected at selected visits only if a participant has consented to future analysis.
- q Plasma samples for PK analysis will be collected predose and at 5, 15, 30, and 60 minutes and 2, 4, 6, 8, 12, and 24 hours postdose for Doses 1 and 2 only. Single samples will be collected predose for other doses and at other visits as indicated. The following windows are allowed:
  - Predose
  - 5 and 15 minutes postdose: ± 3 minutes

- 30 and 60 minutes postdose: ± 5 minutes
- 2, 4, 6, and 8 hours postdose: ± 15 minutes
- 12 and 24 hours postdose: ± 1 hour
- r Vital sign measurements will include blood pressure, pulse rate, respiratory rate, and temperature (collected per local standard of care). For Dose 1 and 2, vital sign measurements will be performed predose, at the end of injection, at 30 (± 10) and 60 (± 15) minutes, at 2 (± 30 minutes), 6 (± 30 minutes), and 24 hours (± 1 hour) postdose. At other dosing visits, vital signs will be measured predose. If multiple assessments are due at the same time, the order of priority should be ECG, vitals, PK, and then other assessments; with PK sampling being performed at the nominal time point.
- s A focused physical examination will be performed (see Section 8.2.2) for Dose 1 and 2 only, ECG will be performed predose and at 30 minutes and 6 hours postdose. For other doses, a single ECG will be performed predose. If multiple assessments are due at the same time, the order of priority should be ECG, vitals, PK, and then other assessments, with PK sampling being performed at the nominal time point.
- t At Dose 1, the required questionnaires will be performed predose. See Section 8.1.6 and 8.1.7.
- u The EOT FibroScan and MRE will be performed prior to the EOT liver biopsy. Participants must be fasting for a minimum of 3 hours prior to the FibroScan and 6 hours prior to the MRE being performed. If Screening MRE is done, it is expected that an MRE is done at EOT. If a clinical site does not have access to the required equipment or technology, MRE assessments would be optional.
- v At ET, a liver biopsy will be optional.
- w Serious AEs and treatment-emergent SAEs will be assessed until 30 days after the last day of study participation. Ongoing SAEs will be followed until resolution or until resolved with sequalae.
- x Participants should be fasting for a minimum of 8 hours prior to selected visits.

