# 4.2. Scientific Rationale for Study Design

As this is the first evaluation of belcesiran in patients with AATLD, safety and tolerability are best assessed via a double-blind, placebo-controlled study. Because AATLD is a rare disease, the use of an unbalanced randomization ratio will minimize exposure of participants to placebo whilst still allowing for an unbiased assessment of safety and maximizing the amount of PD data to be collected.

It is expected that the knockdown of *SERPINA1* mRNA will result in decreased production of Z-AAT in the liver, and hence decreased levels of circulating AAT in serum.

The effect of belcesiran on AATLD will be assessed via changes in the levels of Z-AAT in the liver and serum, as well as by changes in liver histology. Liver biopsy is regarded as the gold standard for the direct assessment of the progression of liver disease over time. The use of 3 parallel cohorts with biopsies scheduled at either weeks 24 or 48 as well as the optional biopsy at week 96 will allow for the evaluation of treatment effect at different timepoints especially since change in liver histology might require a longer treatment period. Biopsy findings will be correlated with changes in non-invasive markers of liver disease and will potentially be supported by "omics" analyses, such as proteomics.

The targeted population includes patients with fibrotic liver disease who are most likely to benefit from a future therapy with belcesiran, and excludes patients with liver impairment or decompensated cirrhosis, as these patients are at higher risk for complications, including those associated with liver biopsy. WOCBP are eligible if they agree to follow the contraception guidelines provided in Section 10.4.2.

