### 8.1.2. Assessment of Fibrosis and Hepatic Z-AAT Content via Percutaneous Liver Biopsy

Percutaneous non-targeted liver biopsies will be performed to assess eligibility to the study and quantify the change in hepatic Z-AAT protein content and histology.

Liver biopsy will be performed according to the study-specific Liver Biopsy Manual. The first biopsy will be performed at Screening once all other eligibility criteria are met, and the participant is qualified for enrollment. The second liver biopsy will be at either 24 weeks (Cohort 1 and 3) or 48 weeks (Cohort 2) after administration of the first dose of the study intervention. Finally, there will be an optional liver biopsy at week 96.

The participant's vital signs will be monitored during the biopsy procedure per local standard of care. As post-biopsy care, the participant will be observed per local standards of care for any signs or symptoms of bleeding, hematoma, and pain.

Liver tissue will be processed on-site, in accordance with the study-specific Liver Biopsy Manual (e.g., snap frozen or formalin-fixed) and sent to a central laboratory for pathology. A clinical report will be generated and sent to the Principal Investigator. In addition, the histology assessment might be supplemented by digital pathology evaluation.

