1 INTRODUCTION

The purpose of this Statistical Analysis Plan (SAP) is to provide a description of the statistical methods to be implemented for the analysis of study data from protocol DCR-A1AT-201, “A Phase 2, Randomized, Double-blind, Placebo-controlled Study Investigating Safety, Tolerability, Pharmacokinetics and Pharmacodynamics of Two Dose Levels of Belcesiran in Patients with Alpha-1 Antitrypsin Deficiency-Associated Liver Disease”. The SAP will be finalized prior to the final database lock. Any deviations from the SAP after database lock will be documented in the final Clinical Study Report (CSR).

The SAP reflects the planned study design as per the latest version of the protocol; however, the Sponsor made the decision to stop the trial prior to the enrollment of Cohort 3 subjects and prior to the completion of the planned study procedures for Cohorts 1 and 2 participants. Cohort 3 and related activity plan will be cancelled. Therefore, the available safety, AAT and biopsy data from Cohort 1 and Cohort 2 will be analyzed for the CSR purpose and there is no analysis planned for Cohort 3.

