Day 757- Post EOT Week 12	757	716	799
Day 841- Post EOT Week 24	841	800	883
Day 925- Post EOT Week 36	925	884	967
Day 1009- Post EOT Week 48	1009	968	1093
Day 1177- Post EOT Week 72	1177	1094	1261
Day 1345- Post EOT Week 96	1345	1262	

Early termination visits for Cohort 2 participants will be assigned to analysis visits according to the following visit windows if participants do not enter the optional treatment period:

Analysis Visit	Target Analysis Day	Low Analysis Day	High Analysis Day
Screening	-35		-1
Day 1	1	1	1
Day 2	2	2	2
Day 3	3	3	9
Day 15	15	10	22
Day 29	29	23	43
Day 57	57	44	71
Day 85	85	72	99
Day 113	113	100	127
Day 141	141	128	155
Day 169	169	156	183
Day 197	197	184	211
Day 225	225	212	239
Day 253	253	240	267
Day 281	281	268	295
Day 309	309	296	323
Day 337	337	324	379
Day 421- Post EOT Week 12	421	380	463
Day 505- Post EOT Week 24	505	464	547
Day 589- Post EOT Week 36	589	548	631
Day 673- Post EOT Week 48	673	632	757
Day 841- Post EOT Week 72	841	758	925

Day 1009- Post EOT Week 96	1009	926	
-------------------------------	------	-----	--

If the activity is not scheduled to occur at the assigned visit, then the closest scheduled visit for that activity will be assigned. If an ET visit is re-assigned to an analysis visit for which a scheduled visit occurred, then the data from the scheduled visit will be used in the analysis for that time point. For example, if the Dose #4/Day 85 visit occurred as scheduled and then a participant withdrew on Day 90 and came back in for ET assessments, the ET visit will be re-assigned to Day 85 based on the table above; however, the assessments from the scheduled Day 85 visit will be used for analysis of the Day 85 time point.

In addition, the measurements from all last visits will be summarized descriptively for all safety assessments.

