3.4.3 Secondary Endpoints

Analyses of Fibrosis, Steatosis, and Inflammation

Descriptive summaries will be provided for METAVIR scores, and Ishak scores. METAVIR scores are composed of a 2-letter and 2-number coding system that describes activity (A) and fibrosis (F). Ishak scores range from 0 (no fibrosis) to 6 (cirrhosis) and will be analyzed as a continuous variable.

Values and changes from baseline (if applicable) will be presented at each scheduled visit by treatment and overall. Listings of the individual parameters will be provided.

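### SAP 3.1.2 sets no distance limit when placing an early-termination biopsy, so an optional-period biopsy can be summarised as Week 96 many weeks before Week 96

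*SAP*

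**What the plan says.** SAP 3.1.2 first assigns each ET visit to an analysis visit through its window tables. Then, for an assessment not planned at that visit: "If the activity is not scheduled to occur at the assigned visit, then the closest scheduled visit for that activity will be assigned". If the receiving visit took place as planned, "then the data from the scheduled visit will be used in the analysis for that time point". The SAP's only worked example is an ET visit on Day 90, where "the ET visit will be re-assigned to Day 85 based on the table above".

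Under Protocol 1.3, ET visits in the treatment period carry the Day 673 activities apart from dosing. A Cohort 1 schedule footnote says "At ET, a liver biopsy will be optional". In Cohort 2 the biopsy in the Day 673/ET column is likewise optional. Protocol 8.1.2 puts the second biopsy at Week 24 (Cohort 1) or Week 48 (Cohort 2), with an optional one at Week 96.

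For histology, SAP 3.4.3 says: "Values and changes from baseline (if applicable) will be presented at each scheduled visit by treatment and overall". It also promises listings of the individual parameters. SAP 3.1.4 puts scheduled-visit data in tables and figures, and all data, including ET data, in listings. The last-visit summary in SAP 3.1.2 covers safety assessments only, so it does not pick up histology.

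**The concern.** The nearest-visit rule is harmless for assessments repeated every few weeks; the SAP's example moves data by 5 days. Biopsy is different. In Cohort 1 the two post-dose biopsy visits are 504 days (72 weeks) apart, and in Cohort 2 they are 336 days (48 weeks) apart. Most ET days fall in a window with no biopsy, so the rule decides the label, and nothing bounds the distance it may cover.

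The time point is part of what the histology is meant to show. Protocol 4.2 justifies staggered biopsies "especially since change in liver histology might require a longer treatment period", and the secondary endpoints are changes in fibrosis and globules up until Week 96. A biopsy filed under the wrong week misstates the treatment duration it represents. One left out of the by-visit table loses information on an intermediate duration. SAP section 1 keeps biopsy data in the report even though the trial was stopped "prior to the completion of the planned study procedures for Cohorts 1 and 2 participants".

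**Working it through.** **Inputs.** Window tables: SAP 3.1.2. Biopsy days: Protocol 1.3 and 8.1.2 (Cohort 1: Days 169 and 673; Cohort 2: Days 337 and 673). Cohort size: up to 8, randomised 3:1 (SAP 2.2.4).

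**The SAP's own example.** Day 90 lies in the Day 85 window (72–99), a shift of 90 − 85 = 5 days. It reproduces in all four window tables.

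**Rule applied to biopsy.** Choose the biopsy day B that minimises |r − B|, where r is either the actual ET day or the target day of the assigned visit. The labelling error is |ET day − B| / 7 weeks.

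**Week 96 label, optional period, ties set aside:**

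| Cohort | r | First ET day labelled Week 96 | Distances compared | Weeks early |
|---|---|---|---|---|
| 1 | assigned visit | 464 (assigned to Day 505) | 505 − 169 = 336; 673 − 505 = 168 | (673 − 464)/7 = 29.9 |
| 1 | actual day | 422 | 422 − 169 = 253; 673 − 422 = 251 | 251/7 = 35.9 |
| 2 | assigned visit | 548 (assigned to Day 589) | 589 − 337 = 252; 673 − 589 = 84 | (673 − 548)/7 = 17.9 |
| 2 | actual day | 506 | 506 − 337 = 169; 673 − 506 = 167 | 167/7 = 23.9 |

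**Ties.** In Cohort 1, 421 − 169 = 673 − 421 = 252. In Cohort 2, 505 − 337 = 673 − 505 = 168. By assigned visit, a whole window is therefore unresolved: Days 380–463 in Cohort 1 and Days 464–547 in Cohort 2. By actual day, only Days 421 and 505 tie. If a tied window goes to Week 96, the label can be (673 − 380)/7 = 41.9 weeks early in Cohort 1 and (673 − 464)/7 = 29.9 weeks early in Cohort 2.

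**Biopsies nearer the earlier visit.** In Cohort 1, by assigned visit, ET Days 184–379 go to Day 169. The latest, Day 379, is (379 − 1)/7 = 54.0 weeks after first dose and (379 − 169)/7 = 30.0 weeks after the visit it is assigned to. In Cohort 2, Days 380–463 go to Day 337, up to (463 − 337)/7 = 18.0 weeks late. Read assessment by assessment, the precedence rule drops these from the by-visit summary when the scheduled biopsy exists and gives them that label when it does not.

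**ET before the first post-dose biopsy.** The answer depends on whether Screening (SAP target Day −35) counts as a candidate visit, which the SAP does not say.
- If it counts, a Week 24 label can be 13.9 to 14.6 weeks early and a Week 48 label 25.9 to 26.6 weeks early. Post-dose biopsies up to about Day 67–71 (Cohort 1) or Day 151–155 (Cohort 2) would be assigned to Screening.
- If it does not count, the limits are 23.9 and 47.9 weeks.

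**With labels restricted to a visit's own window.** The largest gaps are:
- Day 169, window 156–183: 14 days (2 weeks); window 156–211 without the optional period: 42 days (6 weeks).
- Day 337 in Cohort 2, window 324–379: 42 days (6 weeks).
- Day 673, window 632–715: 42 days (6 weeks).

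**Weight of one biopsy.** A full cohort of 8 at 3:1 has 6 belcesiran and 2 placebo participants, so one biopsy is 1/6 or 1/2 of a cohort-by-treatment cell. With the two cohorts combined (12 and 4), it is 1/12 or 1/4.

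**The case against.** The best defence is that the rule may rarely or never act on a biopsy. The ET biopsy is optional. Protocol 7.1.1 asks participants who stop drug to keep attending scheduled visits, Protocol 7.2 expects withdrawal to be uncommon, and the ET column of the follow-up schedule has no biopsy. SAP 5.2 locks the database after follow-up is complete, which suggests that participants moved into follow-up rather than to ET visits. The analysis is descriptive, without hypothesis tests (SAP 3.1.5), and individual listings will exist. All of this stands. It limits the consequence but does not correct the rule.

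Four stronger readings are tempting, and the documents do not support them.
- A reader might infer that an error of 30 to 36 weeks applies to every label and cohort. That range describes the Cohort 1 optional period; the other cases differ, as shown above.
- A reader might infer that biopsies are discarded. SAP 3.1.4 and 3.4.3 keep them in listings; the loss is from the by-visit summary.
- A reader might infer that ET biopsies will be the main source of late histology because of the early stop. No document gives their number, and it may be zero.
- A reader might take the gaps as differences in exposure. They are study time since first dose; doses received may differ.

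It might also be said that SAP 3.1.4 confines tables to scheduled visits, so re-assigned ET data never enter them. That would sit oddly with a section whose purpose is to re-assign ET visits for analysis. If it were so, every ET biopsy would leave the tables. The SAP needs to say which is meant.

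**Conclusion.** The concern holds for the rule as written. It is a stated rule that gives a wrong time-point label for biopsy, not merely a missing detail. Its clearest effect is an optional-period ET biopsy summarised as Week 96 too early: about 30 to 36 weeks in Cohort 1 and 18 to 24 weeks in Cohort 2, depending on the reference point, and up to about 42 and 30 weeks if the unresolved ties go to Week 96. A Week 24 or Week 48 label on a late ET biopsy arises only when the scheduled biopsy is missing; otherwise the ET biopsy is omitted from the by-visit summary.

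This rests on three assumptions: that re-assigned ET data enter the tables, that precedence works assessment by assessment, and that at least one ET biopsy was taken outside a biopsy visit's window. The practical effect is unknown. In cells this small a single case would matter, and the point should be settled before the tables are produced.

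**What to change.** In SAP 3.1.2, exempt liver biopsy from the nearest-visit sentence. Label an ET biopsy Week 24, 48 or 96 only if it falls inside that visit's own analysis window, which caps the gap at 6 weeks and removes the ties. State that post-dose data are never assigned to Screening. Report any other ET biopsy in a separate ET-biopsy row of the histology tables, with actual weeks since first dose and number of doses received, even when an earlier scheduled biopsy exists. State in SAP 3.1.4 that this row enters the tables.

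The cost is a few lines of SAP text and one extra row per histology table. A scheduled time point may have fewer values, because biopsies taken far from it no longer count towards it.

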3.1.3 Definitions of Baseline and End of Study

Baseline (excluding the variable of serum AAT protein concentration) is defined as the last non-missing assessment prior to the first dose of study drug except for serum AAT where baseline is defined as the mean from all predose AAT measurements.

A participant is considered to have completed the study if he or she has completed all phases of the study (including F/U if applicable), including the last visit or the final scheduled procedure.

The end of the study is defined as the completion of the database lock.

3.1.4 Summary Statistics

In general, summary statistics (number of non-missing values), mean, standard deviation, median, minimum and maximum, Q1, and Q3 values for continuous variables, and number and percentage of participants in each category for categorical variables) will be provided by treatment group and cohort for all variables. The denominator used for the percentage calculation will be clearly defined.

In summary tables and figures, data from scheduled visits, including F/U visits, will be included.

Listings will include all data from scheduled and unscheduled/ET visits.

3.1.5 Hypothesis Testing

No hypothesis tests will be performed due to the early termination of the study. All data including demographic, PD and safety parameters will be summarized using descriptive statistics (n, mean, SD, %CV, geometric mean, geometric %CV, minimum, median, and maximum, Q1 and Q3 for continuous parameters; frequency and percentage for categorical parameters).

3.1.6 Handling of Dropouts and Missing Data Values

As statistical analyses will be descriptive in nature, no missing data will be imputed unless otherwise specified. For the classification of treatment emergent adverse events (TEAE) and concomitant medications, the following imputation rules will be applied:

Dates will be printed in ISO 8601 date format (YYYY-MM-DD). If only year and month are available, date will be displayed as YYYY-MM. If only year, then just YYYY. Dates that are missing because they are not applicable for the subjects will be output as "NA", unless otherwise specified.

Treatment emergent adverse events and concomitant medications with missing start dates will be considered as treatment-emergent unless the partial date excludes that possibility. Otherwise, the first day of the month will be used to impute the missing start day and January will be used to impute missing start month.

The purpose of imputing day and month values is to determine treatment emergence or whether a medication is a prior or a concomitant medication. The imputed value will not be presented in the listings. Only the derived TEAE status and concomitant medication status will be presented.

3.2 Analysis Populations

3.2.1 *Enrolled Population*

The Enrolled Population is defined as all participants who sign the informed consent.

3.2.2 *Safety Population*

The Safety Population is defined as all participants randomly assigned to study intervention and who received at least 1 dose of belcesiran/placebo. Participants will be analyzed according to initial dose received.

3.2.3 *Pharmacokinetic (PK) Population*

The PK Population is defined as all participants randomly assigned to study intervention and who received at least 1 dose of belcesiran and have at least 1 postdose PK assessment.

3.2.4 *Pharmacodynamic (PD) Population*

The PD Population is defined as all participants randomized who received at least 1 dose of belcesiran/placebo and have at least 1 postdose PD assessment.

3.2.5 *Evaluable Population*

The Evaluable Population is defined as all participants randomly assigned to study intervention and who received at least 50% of planned doses of belcesiran/placebo.

The PK and evaluable population will not be considered for the analysis due to the early termination of the study.

3.3 Subject Data and Study Conduct

3.3.1 *Participant Disposition*

Counts and percentages of participants who completed the treatment period, who completed the treatment period but did not complete the follow-up, who completed the study, and who discontinued from the study will be summarized based on the Enrolled Population. Reasons for early discontinuation will also be summarized.

3.3.2 *Demographic and Baseline Characteristics*

The following demographic and baseline characteristics will be summarized:

- Age (years)
- Sex
- Race
- Ethnicity
- Height (cm)
- Weight (kg)
- Body mass index (BMI) (kg/m²)
- F1, F2, F3 and F4

- AST
- ALT
- Serum AAT
- Receiving augmentation therapy

Demographic and baseline characteristics will be summarized with descriptive statistics or counts and percentages of participants as appropriate by treatment and overall, based on the Safety Population.

3.4 Safety & Efficacy Assessment

3.4.1 Primary Endpoint for Cohorts 1 and 2

Safety Analysis:

All safety analyses will be performed on the Safety Population. The details of the safety analysis are described in section 3.7.

Serum AAT Concentrations Analysis:

Serum AAT protein concentration observed data, absolute change from baseline, and percent change from baseline will be summarized with descriptive statistics by treatment and time point, based on the PD Population.

The data from the date of and onwards of augmentation therapy received will be excluded from the analysis. The augmentation therapy includes Prolastin® and Glassia®.

Correspondingly, figures for observed serum AAT protein concentration longitudinal trajectory, absolute change from baseline, and percent change from baseline will be presented by line plot (mean \pm standard error (SE)) at the individual level and at the cohort level using the linear scale. Figures will include all study periods, relevant references and legends.

The serum AAT concentration will be analyzed by using a linear log-normal regression model by combining Cohort 1 and Cohort 2 together. The linear log-normal regression will include treatment, baseline value and randomized stratification factor for fibrosis types (F1/F2, F3 and F4) as covariate and the change from baseline in serum AAT as the response variable.

The sample SAS code is as follows.

```
/******  
datain=Input data set  
TRT= Treatment (0-Placebo, 1-Belcesiran 210 mg)  
FIB= Fibrosis types (F1/F2, F3, and F4)  
BASE=Baseline serum  
CHG= Serum change in Week 24 from baseline  
*****/  
proc genmod data=datain;  
class TRT FIB;  
model CHG = TRT BASE FIB / dist=normal link=log;  
lsmeans TRT/ PDiff CL alpha=0.05;  
run;
```

The least square mean difference between the Belcesiran 210 mg and Placebo, standard error, and the confidence interval will be reported.

The P-value will not be reported since the hypothesis test will not be performed.

3.4.2 Primary Endpoint for Cohort 3

There are no data for Cohort 3 due to the early termination of the study prior to enrolling participants in this cohort. Therefore, no analysis is planned for Cohort 3.

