The 210 mg q4w dosing regimen was selected to target a near-maximal PD response. From the simulations, the mean reduction in serum AAT was predicted to be approximately 82% by Week 24 (90% prediction interval [PI]: -59.1% to -98.8%). A lower dose of 50 mg q4w was included to better characterize the dose-exposure-response relationship of belcesiran and its safety profile over a range of serum AAT reduction. Following the administration of 50 mg q4w, the mean reduction in serum AAT was predicted to be approximately 65% (90% PI: -44.5% to -82.4%) by Week 24. Simulations predicted a serum AAT reduction of at least 50% by Week 24 in about 90% of the participants receiving 50 mg q4w dose, suggesting a 50% reduction in hepatic AAT production. It has been shown that adults with the SERPINAI PiMZ genotype, which leads to an approximately 50% reduction in hepatic Z-AAT production, have lower levels of serum transaminases, fewer AAT inclusions in liver, and lower liver stiffness than adults with the PiZZ genotype, although higher than adults without the PiZ variant (Schneider et al, 2020). Therefore, the 50 mg q4w dose, which is predicted to reduce hepatic Z-AAT production (and hence the downstream serum Z-AAT) by at least 50% in the majority of study participants with AATLD, may offer some clinical benefits to most of the participants receiving this dose while expanding the range of PD response for dose-exposure-response characterization.

Monthly dose frequency has been selected for Cohorts 1 and 2 to maximize potential PD response. The first 6 months dosing in Cohort 3 will also be monthly after which patients will shift to quarterly dosing. The rationale for exploring an alternative dosing regime is out of consideration for patient burden. For the high dose explored, simulations suggest that reducing dose frequency after steady state would only have a minor effect on the PD response.

In summary, the two belcesiran doses included in the clinical protocol (210 mg and 50 mg) are predicted to result in a range of PD response that would allow for adequate characterization of belcesiran dose-exposure-response in patients with AATLD.

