# 9.3.1.2. Analysis of Serum and Liver Z-AAT Concentrations

The primary endpoint for Cohort 3 of this study is the percentage change from baseline in serum and liver Z-AAT protein concentration at week 24.

The primary endpoint for Cohort 3 will be analyzed by using a linear log-normal regression model. Statistical testing for the primary endpoint of Cohort 3 will be carried out using the Hocheberg testing procedure for the following comparisons: (active high dose vs. placebo) and (active low dose vs. placebo). The linear log-normal regression model will include treatment, baseline value (log transformed) and randomization stratification factor of fibrosis types (F1, F2, F3, and F4) as covariates.

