The study will include 3 cohorts. In Cohorts 1 and 2 there will be up to 8 participants in each cohort (randomization scheme ratio of 3:1 active: placebo). The sample size for Cohort 1 and Cohort 2 is based on clinical consideration rather than statistical power calculation.

The primary endpoint for Cohort 3 of this study is the percentage change from baseline in serum and liver Z-AAT protein concentration at week 24. Assuming the percentage change from baseline is 80%, 60% and 10% in the active high dose group, active low dose group and placebo group respectively, and the standard deviation is 0.5 for all three groups, a sample size of 10 participants per treatment group will provide at least 80% power to detect a statistically significant difference between active high dose group and placebo, and between active low dose group and placebo, at an overall 1-sided significance level of 0.05.

The F1/F2, F3, and F4 fibrosis types will be used as randomization stratification factors for all 3 cohorts.

2.3 **Study Endpoints**

2.3.1 *Primary Endpoints*

The primary endpoints for Cohorts 1 and 2 are:

- The incidence and nature of treatment emergent adverse events (TEAEs), and the change from Baseline in pulmonary function tests (PFTs), 12-lead electrocardiograms (ECGs), physical examination (PE) findings, vital signs, and clinical laboratory tests
- Changes from baseline to weeks 24 (Cohort 1)/ 48 (Cohort 2) in serum AAT protein concentrations

The primary endpoints for Cohort 3 are:

- Change from baseline to week 24 in serum AAT protein levels
- Change from baseline to week 24 in liver AAT protein levels

2.3.2 *Secondary Endpoints*

The secondary endpoints are:

- PK profile of belcesiran
- Change from baseline up until week 96 in liver fibrosis
- Change from Baseline up until week 96 in diastase-resistant PAS-positive AAT globules

2.3.3 *Exploratory Efficacy Endpoints*

The exploratory endpoints are:

- Change from Baseline up until week 96 in FibroScan® score
- Change from Baseline up until week 96 in enhanced liver fibrosis (ELF) score
- Change from Baseline up until week 96 in cytokeratin 18 (CK-18)

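### SAP 3.4.1 puts a log link on change from baseline in serum AAT, so its only adjusted treatment comparison cannot fit the fall expected on belcesiran

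*SAP*

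**What the plan says.** SAP 3.4.1 names a linear log-normal regression for serum AAT, combining Cohorts 1 and 2, with treatment, baseline and fibrosis stratum (F1/F2, F3, F4) as covariates.

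- The prose takes "the change from baseline in serum AAT as the response variable".
- The sample code agrees. It defines "CHG= Serum change in Week 24 from baseline" and fits "model CHG = TRT BASE FIB / dist=normal link=log". Neither text nor code reverses the sign.
- The promised output: "The least square mean difference between the Belcesiran 210 mg and Placebo, standard error, and the confidence interval will be reported". No p-value is to be reported.
- SAP 2.3.1 gives the primary PD endpoint for these cohorts as "Changes from baseline to weeks 24 (Cohort 1)/ 48 (Cohort 2) in serum AAT protein concentrations".
- Protocol 4.2 expects less Z-AAT production in the liver, "and hence decreased levels of circulating AAT in serum". For 210 mg every 4 weeks, Protocol 4.3 predicts a mean reduction of about 82% by Week 24 ("90% prediction interval [PI]: -59.1% to -98.8"%).
- Protocol 9.3.1.2 uses the same model name for another cohort: "The primary endpoint for Cohort 3 will be analyzed by using a linear log-normal regression model". It log-transforms the baseline and mentions no log link on change.

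All other serum AAT output in the SAP is descriptive.

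**The concern.** A log link constrains the fitted mean to be positive, while the response is a signed change that should be clearly negative on active drug. The model therefore fails in the situation the trial was designed to show. It is the only covariate-adjusted between-arm estimate for a primary PD endpoint, in the only cohorts that will be analysed.

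Two further mismatches follow from the same line of code:

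- A normal distribution with a log link is not a log-normal regression. Taking that name literally does not help, because the log of a negative change is undefined.
- Under a log link, the LSMEANS contrast is a difference of logs (a log ratio of mean changes), not the LS mean difference that the text promises.

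**Working it through.** **Plan's own figure.** The SAP gives no expected estimate, precision or power for this model, and SAP 2.2.4 says Cohorts 1 and 2 were not sized by a power calculation. There is nothing to reproduce, so the check is algebra with an illustration.

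**Inputs from the documents**
- Model and response: SAP 3.4.1.
- Two cohorts of up to 8, randomized 3:1, so at most 12 belcesiran and 4 placebo: SAP 2.2.1.
- Change on 210 mg: mean -82%, 90% prediction interval -59.1% to -98.8%: Protocol 4.3. This models monthly dosing on healthy-volunteer data and is used here for direction.

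**Assumptions (not in the documents)**
- Baseline mean 30 units; placebo change -10%, 0% or +5%.
- Belcesiran SD about 12 points, from the interval width: (98.8 - 59.1) / (2 x 1.645) = 12.1.

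**Step 1: algebra.** The model sets mu_i = exp(x_i'b), so mu_i > 0. The derivative of the normal log-likelihood in the direction that shifts only the belcesiran arm is

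sum over belcesiran participants of (CHG_i - mu_i) x mu_i / s2.

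If every belcesiran CHG_i is below 0, each term is a negative number times a positive one. The sum is negative at every value of b and never reaches 0. The likelihood keeps rising as the belcesiran means are pushed towards 0, so there is no finite estimate. This does not depend on baseline, SD, sample size, class coding or the sign of the placebo change.

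**Step 2: one participant.** With baseline 30 and an 82% fall, CHG = 30 x (-0.82) = -24.6.

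| Fitted mean mu | (CHG - mu) x mu | (CHG - mu)^2 |
|---|---|---|
| 10 | -346 | 1197.2 |
| 1 | -25.6 | 655.4 |
| 0.01 | -0.246 | 605.7 |
| limit 0 | 0 | 605.2 |

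The fit improves all the way to the boundary and stops 24.6 units from the data. At the interval limits the changes are 30 x (-0.591) = -17.7 and 30 x (-0.988) = -29.6, with the same result.

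**Step 3: simulated trials, 12 versus 4, with treatment, baseline and stratum in the model**
- *Set A:* 9 scenarios x 200 = 1,800 data sets. Baseline SD 6, placebo SD 10 points, stratum mix 60/25/15%. Mean reductions were 82% and 59.1% (SD 12 points) and 98.8% (SD 1 point). Direct least squares from 9 starting points gave a belcesiran mean of at most 0.004 units in every data set, against true means of about -24, -18 and -29.5. At the 82% reduction, the fitted placebo mean also fell to about 0 in 65%, 13% and 3% of data sets (placebo -10%, 0%, +5%).
- *Set B:* 3 x 300 = 900 data sets. Reduction 82% (SD 12 points), placebo SD 15 points, strata split 8/5/3. Iteratively reweighted least squares failed in 300 of 300 for each placebo assumption. With a general optimiser, the 5th to 95th percentiles of the treatment coefficient were -104 to +9 (placebo -10%) and -286 to +12 (placebo 0%). The median residual sum of squares was 99.5% to 100% of that from predicting zero for everyone.

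**Step 4: workable models on the same data.** In Set A at 82% and placebo 0%, identity-link ANCOVA on CHG gave a mean LS difference of -24.4 (raw difference -24.5), and the model for log(post/baseline) gave a median geometric mean ratio of 0.14. In Set B, log(AAT) with log baseline gave a median ratio of 0.149 (median 95% limits 0.045 and 0.449) at placebo 0%, and 0.165 (0.051 and 0.504) at placebo -10%.

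**The case against.** The best case on the other side concerns weight rather than mechanism.

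- **Little rests on the model.** There are no tests or p-values, Cohorts 1 and 2 were never powered, the trial stopped early, and observed, absolute and percent change are summarised by arm and visit. This stands and limits the harm to one adjusted estimate and its interval.
- **The SAP may not intend a model.** SAP 3.1.5 calls for descriptive statistics and SAP 3.6 plans no PD analysis. The tension is real, but neither section cancels the explicit commitment in 3.4.1 to report the estimate, standard error and interval.
- **The code is only a sample,** and SAP 7 leaves programming details to a separate document. The prose names the same response, so it offers no working alternative. If CHG were a ratio to baseline the code would fit (a check returned 0.18 for a true 0.18), but a ratio is not a change.
- **A programmer could reverse the sign.** The SAP does not say so, and it is not a safe rescue. Under the Set B assumptions, the placebo mean reduction was zero or below in 10%, 50% and 75% of trials (true placebo change -10%, 0%, +5%), which moves the difficulty to the placebo arm.
- **The simulations assume the answer.** Partly true: with a mean of -59.1% and an SD of 12 points, zero lies 59.1/12 = 4.9 SD away, so wholly negative changes are built in. The algebra is the evidence, and it is conditional on all belcesiran changes being negative.
- **PROC GENMOD was not run.** Correct. Whether SAS would stop, warn or print numbers is untested.
- **Week 24 is a sensible pooled visit,** since both cohorts are still on monthly dosing and Cohort 2 Week 48 is summarised descriptively. Accepted: the visit needs a clarifying sentence only.

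**Conclusion.** The concern holds. As written, the SAP 3.4.1 model has no finite treatment estimate whenever all belcesiran changes are negative, which is what the protocol predicts. Anything the software printed would reflect its stopping rule. The model's name, its link and its promised output also describe three different analyses.

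The non-existence result is exact and rests only on the sign of the belcesiran changes. The simulated sizes are illustrations on assumed baseline, variability and placebo values. What is lost is the one adjusted between-arm estimate and confidence interval for serum AAT; the descriptive results are unaffected. It must be fixed before unblinding, because choosing scale, link and visit after seeing at most 12 versus 4 participants would be post hoc.

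**What to change.** Remove the log link on CHG and specify one of these before participant-level unblinding:

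1. **To match the log-normal name:** regress log(AAT at the analysis visit), or log(AAT/baseline), on treatment, log baseline and fibrosis stratum (F1/F2, F3, F4) with an identity link. Back-transform to a geometric mean ratio and percent difference with confidence interval. Log baseline is a modelling choice here, since Protocol 9.3.1.2 covers Cohort 3 only.
2. **To keep the promised LS mean difference:** leave CHG as the response and set `link=identity` (ANCOVA) with treatment, baseline and fibrosis stratum.

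State that Week 24 is the pooled visit, if that is intended, and whether Cohort 2 Week 48 gets its own model or stays descriptive. Align SAP 3.1.5 and 3.6 with the choice. If the sponsor wants description only, delete the model and the sentence promising its output.

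The cost is a few lines of SAP text and SAS code, with no new data. If the database is already locked, record the replacement as a deviation in the CSR, as SAP 1 requires.
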